## **List of Abbreviations**

### **LIST OF ABBREVIATIONS**

AE	Adverse Event/Adverse Experience
CFR	Code of Federal Regulations
CRF	Case Report Form
DSMB	Data and Safety Monitoring Board
FDA	Food and Drug Administration
GCP	Good Clinical Practice
HIPAA	Health Insurance Portability and Accountability Act
IB	Investigator's Brochure
IND	Investigational New Drug Application
IRB	Institutional Review Board
PHI	Protected Health Information
PI	Principal Investigator
SAE	Serious Adverse Event/Serious Adverse Experience
SOP	Standard Operating Procedure

## Study Summary

Title	Outpatient Foley catheter compared to usual inpatient care for cervical ripening: A non-randomized prospective study
Running Title	Outpatient vs. inpatient cervical ripening
Protocol Number	14-008988
Phase	Pivotal
Methodology	Prospective
Overall Study Duration	24 months
Subject Participation Duration	4-36 hours
Single or Multi-Site	Single site
Objectives	To compare the length of pre-delivery hospitalization in pregnant women undergoing cervical ripening with a Foley catheter in the outpatient setting compared with standard methods administered in the inpatient setting.
Number of Subjects	40 Outpatient Foley Subjects + 160 standard of care subjects Total of 400 women and their babies
Diagnosis and Main Inclusion Criteria	Pregnant women at $\geq$ 37 weeks gestation who are scheduled for induction of labor and who have an unfavorable cervical exam (Bishop score <9 and cervical dilation <3cm)
Study Product, Dose, Route, Regimen	The Foley catheter is a single balloon catheter that is placed transcervically by a provider and inflated with 60cc of normal saline. It mechanically dilates the cervix to 3-4cm over several hours.
Duration of Administration	The device will remain in place until it passes through the cervix, generally when the cervix is dilated to 3-4 cm, which typically occurs 3-12 hours after placement.
Reference therapy	Cervical ripening in the inpatient setting with either a Foley catheter and/or vaginal misoprostol 25 mcg tablets every 4 hours.
Statistical Methodology	The mean time of pre-delivery hospitalization between outpatient Foley catheter and inpatient usual care groups will be compared using a two sample t-test or the nonparametric equivalent Wilcoxon rank sum test. Secondary endpoints will be compared using two sample t-tests or the nonparametric equivalent Wilcoxon rank sum test for continuous endpoints or the chi-Square or Fisher's exact test for categorical endpoints.

## 1 Introduction

This document is a protocol for a human research study. This study will be carried out in accordance with the procedures described in this protocol, applicable United States government regulations, and Mayo Clinic policies and procedures.

### 1.1 Background

In 2012, 23% of pregnant women underwent induction of labor in the United States [1]. Induction of labor is the use of pharmacologic and/or mechanical methods to initiate labor [2]. Cervical ripening generally refers to the early part of labor induction in cases where methods are required to achieve a “favorable cervix,” variably defined at  $\geq 6$  or  $\geq 8$  by Bishop score (a scoring system based on 5 components including cervical dilation, effacement, position, consistency, and fetal station with a range of 0-13) [3]. Cervical ripening in women with unfavorable cervical examinations has been shown to decrease cesarean delivery compared with oxytocin alone [4]. Vaginal prostaglandins and the transcervical catheter are the two most common methods of cervical ripening. Cervical ripening can be a lengthy process, though often a passive one requiring little provider intervention. It is conventionally performed in an inpatient setting; however, there has been an increasing amount of research investigating cervical ripening in the outpatient setting [5]. Although cervical ripening has traditionally been performed in the inpatient setting, the medical necessity of this practice is unproven [6]. Increasing the time a woman spends in her home environment has the potential to decrease the length of hospital stay and associated healthcare costs as well as improve maternal satisfaction.

A recently published study comparing inpatient versus outpatient cervical ripening with vaginal prostaglandin E2 gel found no difference in clinical outcomes including oxytocin use, cesarean delivery, and vaginal delivery within 24 hours [6]. Importantly, though, women in the outpatient group were more likely to have tachysystole (more than 5 contractions in 10 minutes) with fetal heart rate changes, and less than half remained at home overnight. The authors state, and we agree, that prostaglandins may not be the safest agent for outpatient cervical ripening. Compared to prostaglandins, the Foley catheter is associated with a decreased rate of uterine tachysystole with fetal heart rate changes [7]. There is no difference in the rate of chorioamnionitis, endometritis, undelivered women at 24 hours, meconium passage, or serious maternal or neonatal morbidity [7]. The Foley catheter has been shown to be comparable to prostaglandins with regard to cesarean delivery rates [8]. Thus, because the Foley catheter does not cause tachysystole with fetal heart rate changes and does not require interval dosing, it is a potentially promising option for outpatient cervical ripening.

A recent retrospective review of 1,905 low risk women undergoing cervical ripening with the Foley catheter examined adverse effects occurring in the first 12 hours after Foley placement [9]. Of the 1,905 women studied, only 3 underwent cesarean delivery following Foley placement and post-placement monitoring (1 for face presentation and 2 for arrest of dilation). All 3 women would have been excluded from an outpatient trial based on rupture of membranes or spontaneous labor at the time of Foley placement. There were no stillbirths and no cesareans performed for abruptio or nonreassuring fetal heart tracing. Based on this study, the Foley catheter is a safe method of cervical ripening with no reported adverse fetal or maternal effects and should be considered for use in the outpatient setting.

Sciscione et al. performed the first prospective randomized controlled trial comparing the use of a Foley catheter in the inpatient versus outpatient setting [10]. A total of 111 women were enrolled; 61 were randomized to the outpatient setting. All women had a number 16 Foley catheter filled with 30cc of sterile saline placed by sterile speculum exam. The primary outcome was difference in Bishop score from the first cervical exam to the cervical exam the next morning. They found no significant difference in the change in Bishop score, pain scores, or total induction time between the groups. The inpatient admission time was 9.6 hours longer in the inpatient group compared to the outpatient group. Only 8% (n=5) returned overnight for either rupture of membranes or labor.

A similar, more recent trial by Henry et al. compared outpatient Foley catheter placement to inpatient PGE2 vaginal gel in 101 women [11]. The outpatient group spent 11.1 fewer hours in the hospital prior to delivery compared to the inpatient group ( $p < .001$ ). They also felt less pain and got more sleep during cervical ripening. Oxytocin was required for induction more often in the outpatient group. No adverse neonatal or maternal outcomes were associated with outpatient Foley catheter allocation. Only one woman in the outpatient group returned to the hospital earlier than scheduled (for regular, painful contractions).

The trials by Sciscione et al. and Henry et al. have limitations, though. First, neither utilized a standard protocol for labor induction. Second, the inpatient control group was allocated to either Foley usage alone (Sciscione et al.) or prostaglandin PGE2 gel alone (Henry et al.). We believe the most appropriate comparison group is “usual care” wherein women may receive either the Foley catheter or prostaglandins based on patient and provider preference.

The use of a Foley catheter for cervical ripening in the outpatient setting has the potential for substantial advancement to the induction process for the patient, provider, and healthcare system. The Foley catheter is a safe, inexpensive method of cervical ripening that causes less fetal heart rate effects than other ripening methods [7, 8]. Women may find gratification by being in their home environment during more of their labor course [12]. Providers and healthcare systems may be better able to allocate their resources with decreased length of stay during the early induction phase. A 2013 Cochrane review of outpatient cervical ripening concluded that more studies are required to demonstrate its efficacy and safety in this setting [5]. Our study will provide additional evidence of safety and efficacy to transition cervical ripening to the outpatient setting.

## 1.2 Investigational Agent

The Foley catheter is a device used to achieve cervical ripening to start labor induction. It is the most common mechanical method used for cervical ripening in the third trimester. It is a single balloon catheter placed transcervically by a provider, either digitally or using a speculum for visualization. The balloon is placed above the internal os but below the fetal head, amniotic membranes, and placenta and is inflated with 30-80 mL of normal saline. Traction is placed on the catheter, either by taping the catheter to the patient’s thigh and/or intermittently by a provider. Over several hours, the balloon gradually dilates the cervix. The catheter is expulsed when the cervix is 3-4 centimeters. At this dilation, oxytocin (Pitocin) is much more effective.

## 1.3 Clinical Data to Date

Please refer to section 1.1 and 1.2.

## 1.4 Dose Rationale and Risk/Benefits

Only one Foley catheter is placed during a patient's labor induction course. The single balloon can be filled with 30-80 mL of normal saline. Our equipment best facilitates 30-60 mL. A study by Delaney et al. demonstrated that inflation with 60 mL increased the likelihood of delivery within 12 hours compared to 30 mL without any adverse maternal or neonatal outcomes [13]. Therefore, 60 mL was elected for this study.

Common adverse effects of transcervical Foley catheters include discomfort and vaginal spotting. The patient may feel uncomfortable during placement of the Foley catheter and while the Foley catheter is in place. Similarly, women in the inpatient group can expect discomfort during the initiation of their labor induction as well, whether with the Foley catheter or vaginal misoprostol. Pain control options as described elsewhere in this document will be available for patient comfort. Available data suggests that the Foley catheter is tolerable from a pain perspective. Pennell and colleagues evaluated pain associated with the Foley catheter and found that pain with insertion was rated as 4/10 and pain during cervical ripening was 2/10 [14]. Overall satisfaction with induction of labor for Foley catheter was 8/10, which was equivalent to the other cervical ripening agents studied.

Patients may also commonly experience vaginal spotting after placement of a Foley catheter. This is typically from cervical manipulation rather than clinically significant placental abruption. In the majority of cases, these etiologies can be distinguished by experienced clinical evaluations. If there is suspicion that vaginal bleeding represents placental abruption, the patient will be excluded from the trial and kept in the inpatient setting until delivery. The amount of blood lost from vaginal spotting is not clinically significant and is common during induction of labor in the inpatient setting.

Less likely risks include the following: artificial or spontaneous rupture of membranes, initiation of spontaneous labor, and placental abruption, both clinically significant and insignificant. The patient will be educated regarding these risks. Should any of these events be diagnosed while the patient is in the Family Birth Center for post Foley monitoring, she will be kept as an inpatient until delivery and excluded from the trial. Should any of these occur at home, the patient will return immediately to the Family Birth Center as outlined in both verbal and written instructions.

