#### **4.2 Exclusion Criteria**

1. New diagnosis requiring immediate hospitalization for monitoring (such as preeclampsia)
2. Vaginal bleeding
3. Active labor
4. Premature rupture of membranes as determined by positive ferning and as supported by pooling of fluid in the vaginal vault.
5. Uterine tachysystole (>5 contractions in 10 minutes)
6. Nonreassuring fetal heart tracing before or after Foley placement
7. Chorioamnionitis or maternal fever
8. Intrauterine fetal demise
9. Contraindication to vaginal delivery, relative or absolute (i.e. transfundal uterine surgery)
10. Abnormal placentation including a low lying placenta
11. Prior cesarean delivery
12. Intrauterine growth restriction (growth <10th percentile by formal ultrasound)
13. Known major fetal anomaly
14. Human immunodeficiency virus, Hepatitis C, or active herpes infection
15. Maternal cardiopulmonary disease requiring cardiac monitoring during labor
16. Pregestational diabetes
17. Rh isoimmunization
18. Non-English speaking

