Finally, the pregnant woman may become excluded from study shortly after arrival to the Family Birth Center for initiation of the planned induction of labor. Any of the above-listed reasons (vaginal bleeding, spontaneous labor, premature rupture of membranes, etc) diagnosed at presentation will be reason to exclude the woman from participation. Furthermore, *after* Foley catheter placement, a patient may be excluded from the trial should any of the following occur:

1. She is diagnosed with a condition that requires immediate admission for induction of labor (such as gestational hypertension or preeclampsia)
2. She develops vaginal bleeding more than spotting that is clinically concerning for placental abruption
3. She spontaneously labors
4. She undergoes premature rupture of membranes
5. The post-placement fetal heart tracing is non reassuring such that outpatient management is not recommended
6. She develops a fever and/or chorioamnionitis

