#### **4.4.2 Data Collection and Follow-up for Withdrawn Subjects**

Data will not be collected from women who electively withdraw from the study. Data will be collected on all women who are randomized to a treatment group. Should patients from the outpatient group cross over to the inpatient group (i.e. if they meet exclusion criteria), analysis will be by intention to treat.

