## 7.4 Subject Population(s) for Analysis

We will analyze all subjects who were randomized in the randomized control trial design stage of the study, except those who electively withdrew from the trial. We will analyze all subjects enrolled in the prospective stage of the study, who do not electively withdraw.

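### Sections 1.4, 4.2 and 4.4.1 exclude women from the trial for events after Foley placement, while 4.4.2 and 7.4 keep them in the analysis; the wording needs reconciling, and the data rule in 4.4.2 needs updating

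*Combined protocol and SAP*

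**What the plan says.** Several places in the combined protocol and SAP take a woman out after the catheter is in.

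- Section 1.4, on suspected abruption: "the patient will be excluded from the trial and kept in the inpatient setting until delivery". On membrane rupture, labor or abruption diagnosed during post-Foley monitoring: "she will be kept as an inpatient until delivery and excluded from the trial". Both are mandatory.
- Section 4.4.1, under the heading on withdrawal, is permissive: after placement "a patient may be excluded from the trial should any of the following occur". Six events follow: a condition needing immediate admission, bleeding concerning for abruption, labor, membrane rupture, a nonreassuring tracing, and fever or chorioamnionitis. The paragraph opens with "the pregnant woman may become excluded from study shortly after arrival to the Family Birth Center", so it concerns events in the unit around placement.
- Section 4.2, item 6, lists as an exclusion criterion "Nonreassuring fetal heart tracing before or after Foley placement".

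Two places keep the same women in.

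- Section 4.4.2, on outpatients who cross over to inpatient care: "if they meet exclusion criteria), analysis will be by intention to treat".
- Section 7.4: "We will analyze all subjects enrolled in the prospective stage of the study, who do not electively withdraw".

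On data, Section 4.4.2 says: "Data will be collected on all women who are randomized to a treatment group". The current stage, described in the Study Summary and Section 3.1, is not randomized.

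**The concern.** A woman cannot be both excluded from the trial and analyzed in it. The exclusion rules also differ in force, mandatory in 1.4 and permissive in 4.4.1. Section 4.4.1 uses the same exclusion language for a woman who declines participation after placement, and 4.4.2 collects no data from elective withdrawals. One form of words therefore covers women who leave the dataset and women who should stay in it.

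The safety comparison is what is at stake. Section 3.4 makes the intrapartum complications of Section 3.3 IV.A primary safety outcomes, and some of these are also grounds for exclusion. Suspected abruption is the clearest case. If someone abstracting charts followed 1.4, the comparison would omit some of the events it is meant to count. Section 8.2 would still have them recorded as adverse events, but a between-group comparison depends on who is in the analysis set.

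**Working it through.** **1. The plan's own figure.** Inputs from Section 7.2: 40 and 160 women, means of 12 and 16 hours, SD 8 hours, two-sided 0.05. The standardized difference is (16 − 12)/8 = 0.5. The noncentrality is 0.5 × √(40 × 160/200) = 0.5 × 5.657 = 2.83. The normal approximation gives Φ(2.83 − 1.96) = 80.7%, and the noncentral t gives 80.4%. The stated 80% reproduces.

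**2. Which post-placement events in 4.4.1 are also safety outcomes.**

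| Event in 4.4.1 | Outcome in 3.3 IV.A or 3.4 | Overlap |
|---|---|---|
| 1. Condition needing immediate admission | none listed | none |
| 2. Bleeding concerning for abruption | suspected or confirmed abruption; heavy vaginal bleeding | clear |
| 3. Labor | none listed | none |
| 4. Membrane rupture | none listed | none |
| 5. Nonreassuring tracing | category II or III tracing | partial: the outcome also requires in utero resuscitation |
| 6. Fever or chorioamnionitis | intrapartum fever; chorioamnionitis | partial: the outcome also covers events later in labor |

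Three of the six items overlap, one clearly and two in part. Of the three monitoring events named in Section 1.4, only abruption is a listed safety outcome.

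**3. Size for safety, if the exclusion wording were followed.** The documents give no event rate for the hour of monitoring after placement (Section 3.1 IV.H), so every count and rate here is an assumption. One woman is 1/40 = 2.5 percentage points. The worst case has equal true rates in both groups, every outpatient event falling between placement and dismissal, and no control event removed:

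- 1/40 against 4/160 (2.5% each, difference 0) becomes 0/39 against 4/160, a difference of −2.5 points.
- 2/40 against 8/160 (5.0% each, difference 0) becomes 0/38 against 8/160, a difference of −5.0 points. The exact 95% interval for the outpatient arm moves from 0.6%–16.9% to 0%–9.3%.

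The chance that at least one of 40 outpatients raises the question is 1 − (1 − p)^40: 33.1% at p = 1%, 63.7% at 2.5% and 87.1% at 5%.

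**4. Power.** Dropping two outpatients and their eight matched controls leaves 38 and 152. The noncentrality is 0.5 × √(38 × 152/190) = 2.76, and the noncentral t gives 78.3%. Keeping all 160 controls gives 78.7%.

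**5. Length of stay.** Suppose the full outpatient group has mean 12 hours and a fraction f with mean m is dropped. The remaining mean is (12 − f·m)/(1 − f). With f = 0.05 and m = 16 it is 11.79, and the apparent reduction rises from 4.0 to 4.2 hours. If m is below 12, the apparent reduction falls instead. The excluded women include some in spontaneous labor and some kept in for other reasons. The documents do not give m, so the sign is open.

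**The case against.** The strongest reply is that the plan already settles the matter. Section 4.4.2 addresses this case by name, the outpatient who crosses over because she meets exclusion criteria, and applies intention to treat. Section 7.4 was rewritten for the prospective stage and removes only elective withdrawals. Section 4.3 takes data from all 400 charts and confines screen failures to women who become ineligible before induction. Section 3.1 VII abstracts endpoints on maternal consent, not on randomization. Section 1.4 is a risk narrative, not an analysis rule. All of this stands. It makes retention the better reading and the outdated sentence in 4.4.2 a small edit. It does not remove the literal conflict.

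A reader might infer more than the documents support:

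- *That the plan will drop these women.* Sections 4.4.2 and 7.4 say otherwise.
- *That only the outpatient arm could lose events.* Sections 4.2 and 4.4.1 refer to Foley placement without naming an arm, and controls may also receive a Foley (Section 3.1 V.B and VI). The loss would fall mainly on outpatients, because all of them have one. No matching exclusion is stated for controls once drug ripening has begun.
- *That the loss would be large.* The examples above are worst cases on assumed counts. The early returns in Section 1.1 (5 of 61 in one trial, one woman in another) happened after dismissal, and Section 3.3 II.C counts such returns as outpatient data. They are not the rate for this conflict. The review of 1,905 women in Section 1.1 reports no stillbirths and no cesareans for abruption or nonreassuring tracing. That is reassuring on serious early harm, but it is not a rate for suspected abruption or fever in the monitoring hour.
- *That the hours saved would be overstated.* The sign cannot be determined.

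**Conclusion.** The contradiction is real and should be corrected, as a matter of wording rather than design. Sections 4.4.2 and 7.4 should govern. The consequence is conditional: if the exclusion wording were followed, suspected abruption would leave the safety comparison, along with some fever, chorioamnionitis and tracing events, mainly from the outpatient group. No size can be fixed beyond 2.5 percentage points per woman in an arm of 40. Power is not the issue: the loss is about 2 points if two women and their controls are dropped. Separately, the data-collection sentence in 4.4.2 does not cover the non-randomized stage and is out of date whichever reading is taken.

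**What to change.** Reconcile the passages in favor of Section 7.4.

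- In 1.4, 4.2 item 6 and 4.4.1, state that, for analysis, a post-placement event ends only the outpatient pathway, and that the woman stays in her enrolled group for the primary and safety analyses.
- In 4.4.2, extend data collection to all women in either stage who do not electively withdraw, other than the pre-induction screen failures defined in 4.3. Without that exception the new sentence would sweep in the roughly 50 consented women whom 4.3 sets aside.
- Report the number of outpatients not dismissed home, with reasons.

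Section 3.1 III.B already ties four controls to each outpatient enrolled, so the matching needs no change. Clinical handling, sample size and tests also stay as they are. The cost is protocol wording and, at most, a few charts that might otherwise have been skipped.
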